4 STUDY INTERVENTION/INVESTIGATIONAL PRODUCT

4.1 Study Product Description

Pretomanid, a nitroimidazooxazine, is a novel TB treatment that is being investigated for use with other TB drugs to shorten and/or simplify regimens to treat either drug-susceptible or resistant disease, which may improve the current high rate of noncompliance for TB treatment. Pretomanid acts by inhibiting *Mtb* cell wall biosynthesis, as well as generating NO.

4.1.1 Formulation, Packaging, and Labeling

For this study, pretomanid 200 mg tablets are white to off-white, oval-shaped tablet debossed with M on one side and P200. The formulation of pretomanid tablets is summarized in [Table 3](#).

Table 3: Pretomanid Formulation

| Ingredient | % | Weight per Unit (mg) |
|---|------|----------------------|
| Pretomanid, Micronized | 25.0 | 200.0 |
| Lactose Monohydrate NF (Foremost FastFlo 316) | 36.8 | 294.4 |
| Microcrystalline Cellulose NF (Avicel PH102) | 29.4 | 235.2 |
| Sodium Starch Glycolate NF (Explotab) | 5.0 | 40.0 |
| Magnesium Stearate NF (Hyqual) | 1.0 | 8.0 |
| Colloidal Silicon Dioxide NF (Cab-O-Sil M-5P) | 0.3 | 2.4 |
| Sodium Lauryl Sulfate USP | 0.5 | 4.0 |
| Povidone USP (PVP K30) | 2.0 | 16.0 |
| Purified Water USP | -- | -- |
| Total | 100% | 800.0 mg |

NF=National Formulary; USP=United States Pharmacopeia.

Note: Water is removed during drug product manufacture.

TB Alliance or its designee will package the study product. Study product will be labeled and supplied according to applicable regulatory requirements.

4.1.2 Product Storage and Stability

The investigator or an approved designee (e.g., pharmacist) will ensure that the study product is stored in a locked, secure area (with access limited to authorized study personnel only) under

recommended storage conditions and in accordance with applicable regulatory requirements. Pretomanid will be stored at 15-30°C (59-86°F).

4.2 Acquisition/Distribution

Pretomanid will be provided by Global Alliance for TB Drug Development according to the terms of the Clinical Trial Agreement between the TB Alliance and NIAID.

Upon request by Division of Microbiology and Infectious Diseases (DMID), pretomanid will be transferred to the following address:

DMID Clinical Materials Services Contract
Fisher BioServices
[name]
[name]
[contact]
[contact]
Email: [contact]

All study products (i.e., pretomanid) will be shipped to the participating sites prior to the start of this study upon request and with prior approval from DMID. Should the site principal investigator (PI) require additional study product during this trial, further instructions are provided in the protocol-specific manual of procedures (MOP).

4.3 Dosage/Regimen, Preparation, Dispensing, and Administration of Study Intervention/Investigational Product

Pretomanid will be administered in the fed state in this study because there is a food effect for the drug. Following an overnight fast of at least 8 hours, participants should start the recommended meal prior to administration of pretomanid [40]. Study participants should eat this meal in 30 ± 10 minutes or less; however, pretomanid should be administered 30 ± 10 minutes after start of the meal. Participants will be given one dose of 200 mg of pretomanid orally under direct supervision with 240 mL of water and a mouth check will be done. All participants will receive the same study product. After dosing, participants will have no food, water, or medications for 2 hours post-dose. If a participant vomits >2 hours post-dose, no redosing or exclusion is required. If a participant vomits within 2 hours of dosing, the participant will be excluded from the study with a plan to replace or rescreen and admit another time, if necessary. When a participant vomits soon after swallowing the drug, part or all of the drug may be lost. There is no way of knowing how much of the drug is already absorbed and redosing with the full dose may affect PK results.

See the protocol-specific MOP Appendices for detailed information on the preparation, labeling, storage, and administration of study product.

4.4 Pre-determined Modification of Study Intervention/Investigational Product for an Individual Participant

Since a single oral dose of pretomanid will be given, there will be no dose modifications.

4.5 Accountability Procedures for the Study Intervention/Investigational Product(s)

Pretomanid will be sent to the DMID Clinical Materials Services (CMS) contractor, and then supplied to the participating sites prior to the start of the study. Should the site PI require additional doses of pretomanid during the trial, further instructions are provided in the protocol-specific MOP.

After receipt of pretomanid, the site PI is responsible for study product distribution and disposition and has ultimate responsibility for drug accountability. The site PI may delegate to the participating site's research pharmacist responsibility for study product accountability. The site research pharmacist will be responsible for maintaining complete records and documentation of study product receipt, accountability, dispensation, storage conditions, and final disposition of the study product. For this study, all study product, pretomanid tablets, should be stored at 15-30°C (59-86°F) in blister-strips comprising a thermoformable-film and a lidding foil configuration. All doses of pretomanid, whether administered or not, must be documented on the appropriate study product accountability record or dispensing log. The sponsor's monitoring staff will verify the participating sites' study product accountability records and dispensing logs per the site monitoring plan.

Unused tablets should be retained within the container in which they are supplied from the CMS. Unused pretomanid tablets will be monitored and released for final disposition. Final disposition of the pretomanid will be determined by DMID and the TB Alliance and communicated to the participating sites by the DMID Clinical Project Manager.

5 SELECTION OF PARTICIPANTS AND STUDY ENROLLMENT AND WITHDRAWAL

The study population will be represented by participants with varying degrees of renal disease as defined by eGFR. Part A will enroll participants into Groups 1A (i.e., 6 healthy matched controls) and 2 (i.e., 6 participants with severe renal impairment and ESRD, not on dialysis).

In this study, participants with renal impairment will be mainly identified from sites' exhaustive database and through referral from local renal clinics. Non-renally impaired participants will be identified from participants who have previously participated in clinical trials and through the community.

The decision to proceed from Part A to Part B will be made jointly by representatives from DMID and TB Alliance. An independent safety review will be carried out by the Safety Monitoring Committee (SMC) and the DMID Medical Monitor. This review will inform the decision to proceed from Part A to Part B.

Part B will be conducted only if the Part A results demonstrate that participants with severe renal impairment and ESRD (not on dialysis) have different exposures to pretomanid that may impact safety or efficacy relative to the exposures of healthy participants. If no difference in PK is observed in Part A, then no further study (Part B) will be recommended.

If the decision is made to conduct Part B, 12 participants (6 participants in each group) with mild and moderate renal impairment will be enrolled in Groups 3 and 4, respectively, along with 12 healthy matched participants (Groups 1B and 1C). Participants in Part B will receive the same single 200 mg dose of pretomanid as participants in Part A.

Participant inclusion and exclusion criteria must be assessed by a study clinician licensed to make medical diagnoses and listed on the Form FDA 1572 as the site PI or sub-investigator.

No exemptions are granted for participant inclusion or exclusion criteria in DMID-sponsored studies. Questions about eligibility will be directed to the DMID Medical Officer.

5.1 Eligibility Criteria

5.1.1 Participant Inclusion Criteria

5.1.1.1 Participant Inclusion Criteria for Patients with Renal Impairment (Groups 2-4)

Participants eligible to participate in this trial must meet all of the following inclusion criteria:

1. Have the ability to understand the requirements of the study and have provided written informed consent¹ before any study-related procedure is performed.

¹*As evidence by signature on an informed consent document approved by the IRB*

2. Agree to abide by the study restrictions.
3. Are between the ages of 18 and 85 years, inclusive, at the time of enrollment.
4. Must have mild, moderate, or severe renal impairment or ESRD, but are not on dialysis. See [Table 1](#) for staging of renal disease.
5. Have no history of chronic tobacco/nicotine usage (i.e., >10 cigarettes per day for 3 months minimum prior to admission).
6. Have QTc interval <460 msec on ECG.
7. Have a BMI of 18 to 40 kg/m² at enrollment.
8. Women of childbearing potential² must use an acceptable contraception method³ for the duration of the study.

²*Not sterilized via tubal ligation, bilateral oophorectomy, bilateral salpingectomy, hysterectomy, implanted contraceptive device placement (permanent, non-surgical, non-hormonal sterilization) with documented radiological confirmation test at least 90 days after the procedure, and still menstruating or <1 year has passed since the last menses if menopausal.*

³*Includes non-male sexual relationships, abstinence from sexual intercourse with a male partner, monogamous relationship with vasectomized partner who has been vasectomized for 180 days or more prior to the participant receiving study product, barrier methods such as condoms with spermicide or diaphragms/cervical caps with spermicide, effective intrauterine devices, NuvaRing®, and licensed hormonal methods such as implants, injectables, or oral contraceptives ("the pill").*

9. If participant is male and capable of reproduction, agrees to avoid fathering a child for the duration of the study by using an acceptable method of birth control⁴.

⁴*In addition to the use of a barrier method (condom) unless vasectomized, acceptable methods of birth control are restricted to a monogamous relationship with a woman who agrees to use acceptable contraception as outlined in inclusion criterion #8, and/or abstinence from sexual intercourse with women.*

10. Women of childbearing potential must have a negative urine pregnancy test within 24 hours prior to receipt of study product.

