Drawing blood may cause transient discomfort and fainting. Fainting is usually transient and managed by having the participant lie down and elevate his/her legs. Bruising at the blood draw site may occur but can be prevented or lessened by applying pressure to the blood draw site for a few minutes after the blood is taken. Rarely, drawing blood may cause infection (thrombophlebitis). The use of aseptic (sterile) technique will make infection at the site where blood will be drawn extremely unlikely.

Peripheral Catheter (if needed)

Inserting a peripheral catheter may cause pain, bleeding, hematoma, vein irritation, infiltration, extravasation, phlebitis, air embolism, and/or infection. Use of proper aseptic technique during the insertion provides protection against infection.

Pregnancy

It is unknown if the study drug poses any risks to an unborn child. As such, females of childbearing potential, i.e., women who have started menses, must agree to use an effective method of birth control for the duration of the study ([Section 5.1.1](#)). Males who are sexually active with a female of childbearing potential must agree not to father a child or donate sperm for the duration of the study.

Other Risks

Personal Health Information (PHI)

Participants will be asked to provide PHI. All attempts will be made to keep this PHI confidential within the limits of the law. However, there is a chance that unauthorized persons will see the participants' PHI. All study records will be kept in a locked file cabinet or maintained in a locked room at the participating sites. Electronic files will be password-protected. Only people who are involved in the conduct, oversight, monitoring, or auditing of this trial will be allowed access to the PHI that is collected. Any publications from this trial will use de-identified information. Organizations that may inspect and/or copy research records maintained at the participating site for quality assurance and data analysis include groups such as the local Institutional Review Boards (IRBs), National Institute of Allergy and Infectious Diseases (NIAID), and FDA.

As required by US law, a description of this clinical trial will be available on <https://clinicaltrials.gov/ct2/show/NCT03896750>. This website will not include information that can be used to identify participants. At most, this website will include a summary of the results.

There may be other risks, discomforts, or side effects that are unknown at this time.

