5.1.1.2 Participant Inclusion Criteria for Healthy Participants (Groups 1A-1C)

Healthy participants eligible to participate in this trial must meet all of the following inclusion criteria:

1. Have the ability to understand the requirements of the study and have provided written informed consent¹ before any study-related procedure is performed.

¹As evidence by signature on an informed consent document approved by the IRB.

2. Agree to abide by the study restrictions.
3. Are healthy male or non-pregnant female, between the ages of 18 and 85 years, inclusive, with normal GFR ≥ 90 at screening.
4. Have no history of chronic tobacco/nicotine usage (i.e., >10 cigarettes per day for 3 months minimum prior to admission).
5. Have a normal QTc interval <460 msec on ECG.
6. Have a BMI of 18 to 40 kg/m² at enrollment.
7. Women of childbearing potential² must use an acceptable contraception method³ for the duration of the study.

²Not sterilized via tubal ligation, bilateral oophorectomy, bilateral salpingectomy, hysterectomy, implanted contraceptive device placement (permanent, non-surgical, non-hormonal sterilization) with documented radiological confirmation test at least 90 days after the procedure, and still menstruating or <1 year has passed since the last menses if menopausal.

³Includes non-male sexual relationships, abstinence from sexual intercourse with a male partner, monogamous relationship with vasectomized partner who has been vasectomized for 180 days or more prior to the participant receiving study product, barrier methods such as condoms with spermicide or diaphragms/cervical caps **with** spermicide, effective intrauterine devices, NuvaRing®, and licensed hormonal methods such as implants, injectables, or oral contraceptives ("the pill").

8. If participant is male and capable of reproduction, agrees to avoid fathering a child for the duration of the study by using an acceptable method of birth control⁴.

⁴In addition to the use of a barrier method (condom) unless vasectomized, acceptable methods of birth control are restricted to a monogamous relationship with a woman who agrees to use acceptable contraception as outlined in inclusion criterion #7, and/or abstinence from sexual intercourse with women.

9. Women of childbearing potential must have a negative urine pregnancy test within 24 hours prior to receipt of study product.

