5.1.2 Participant Exclusion Criteria

5.1.2.1 Participant Exclusion Criteria for Patients with Renal Impairment (Groups 2-4)

Participants eligible to participate in this trial must not meet any of the following exclusion criteria:

1. History of known active TB.

2. History of peptic ulcer disease.
3. Known hypersensitivity to pretomanid or any of the excipients.
4. History of any clinically significant uncontrolled cardiac abnormality (as deemed by the PI).
5. Any clinically significant ECG abnormality at screening¹.

¹*Note: the following can be considered not clinically significant:*

- *Heart rate \leq 50 beats per minute (bpm) (sinus bradycardia with heart rate between 45 and 49, inclusive, is acceptable only in younger athletic participants, as determined by the PI)*
- *Mild first-degree atrioventricular (A-V) block (P-R interval >0.23 seconds)*
- *Right or left axis deviation*
- *Incomplete right bundle branch block*
- *Isolated left anterior fascicular block (left anterior hemiblock) in younger athletic participants*

6. History of, or screening results show a QTc interval \geq 460 msec.
7. Family history of Long-QT Syndrome or sudden death when a cause of death is unknown.
8. Inability to swallow tablets.
9. History of fever or documented fever (oral temperature \geq 100.4°F) in the 48 hours prior to admission to the hospital.
10. Resting pulse rate <50 or >110 bpm at Screening.
11. At Screening, blood pressure \geq 20 mm Hg systolic or >10 mm Hg diastolic above baseline² (sitting).

²*Baseline is most recent blood pressure in the last 3 months.*

12. Current hyperkalemia or hypomagnesemia.
13. Positive result of urine drug screen or alcohol screen prior to hospital admission except for approved prescriptions that are not opiates and benzodiazepines.
14. Significant history of drug and/or food allergies (as deemed by the PI).
15. For women, participant is pregnant (positive test for urine Human Chorionic Gonadotropin [HCG]) at screening or Admission, breastfeeding, or planning to conceive for the duration of the study.
16. Any contraindication to the use of nitroimidazoles, or prior treatment with pretomanid or delamanid.
17. Treatment with strong or moderate CYP3A4 inducers or inhibitors³ within 14 days before admission and during the study⁴.

³Except hormonal contraceptives

⁴In the opinion of the site investigator

NOTE: See [Table 4](#) for a list of drugs known to alter the function of CYP3A4 ([Section 7.1.1](#)).

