5.1.2.2 Participant Exclusion Criteria for Healthy Participants (Groups 1A-1C)

Participants eligible to participate in this trial must not meet any of the following exclusion criteria:

1. History of known active TB.
2. History of peptic ulcer disease.
3. Known hypersensitivity to pretomanid or any of the excipients.
4. History of any clinically significant uncontrolled cardiac abnormality (as deemed by the PI).
5. Any clinically significant ECG abnormality at screening.¹

¹Note: the following can be considered not clinically significant:

- *Heart rate ≤ 50 bpm (sinus bradycardia with heart rate between 45 and 49, inclusive, is acceptable only in younger athletic participants)*
- *Mild first-degree A-V block (P-R interval > 0.23 seconds)*
- *Right or left axis deviation*
- *Incomplete right bundle branch block*
- *Isolated left anterior fascicular block (left anterior hemiblock) in younger athletic participants*

6. Family history of Long-QT Syndrome or sudden death when a cause of death is unknown.
7. Inability to swallow tablets.
8. History of fever or documented fever (oral temperature $\geq 100.4^{\circ}\text{F}$) in the 48 hours prior to admission to the hospital.
9. At Screening blood pressure $> 140/90$ mm Hg or $< 90/65$ mm Hg (sitting).
10. History of, or screening results show a QTc interval ≥ 460 msec.
11. Positive result of urine drug screen or alcohol screen prior to hospital admission except for approved prescriptions that are not opiates and benzodiazepines.
12. Significant history of drug and/or food allergies (as deemed by the PI).
13. Women of childbearing potential with a positive urine pregnancy test within 24 hours prior to receipt of study product.
14. Any contraindication to the use of nitroimidazoles, or prior treatment with pretomanid or delamanid.
15. Treatment with strong or moderate CYP3A4 inducers or inhibitors² within 14 days before admission and during the study³.

²*Except hormonal contraceptives*

³*In the opinion of the site PI*

NOTE: See [Table 4](#) for a list of drugs known to alter the function of CYP3A4 ([Section 7.1.1](#)).

16. Use of St. John's Wort within 7 days prior to admission and during the entire study.
17. Consumption of products containing grapefruit within 5 days prior to dosing until Visit 01N.
18. Donation of whole blood or blood products > 500 mL within 30 days from screening and/or plans to donate during the study or up to 14 days after dosing.

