4.3.1 Participant Inclusion Criteria

Participant Inclusion Criteria for Healthy Participants (Group 1A-1C)

1. Have the ability to understand the requirements of the study and have provided written informed consent¹ before any study-related procedure is performed.

¹*As evidenced by signature on an informed consent document approved by the IRB.*

2. Agree to abide by the study restrictions.
3. Are healthy male or non-pregnant female, between the ages of 18 and 85 years, inclusive, with normal GFR $>$ 90 at screening.
4. Have no history of chronic tobacco/nicotine usage (i.e., $>$ 10 cigarettes per day for 3 months minimum prior to admission).
5. Have a normal QTc interval $<$ 460 msec on ECG.
6. Have a BMI of 18 to 40 kg/m² at enrollment.
7. Women of childbearing potential² must use an acceptable contraception method³ for the duration of the study.

²*Not sterilized via tubal ligation, bilateral oophorectomy, bilateral salpingectomy, hysterectomy, implanted contraceptive device placement (permanent, non-surgical, non-hormonal sterilization) with documented radiological confirmation test at least 90 days after the procedure, and still menstruating or $<$ 1 year has passed since the last menses if menopausal.*

³*Includes non-male sexual relationships, abstinence from sexual intercourse with a male partner, monogamous relationship with vasectomized partner who has been vasectomized for 180 days or more prior to the participant receiving study product, barrier methods such as condoms with spermicide or diaphragms/cervical caps with spermicide, effective intrauterine devices, NuvaRing®, and licensed hormonal methods such as implants, injectables, or oral contraceptives ("the pill").*

8. If participant is male and capable of reproduction, agrees to avoid fathering a child for the duration of the study by using an acceptable method of birth control⁴.

⁴*In addition to the use of a barrier method (condom) unless vasectomized, acceptable methods of birth control are restricted to a monogamous relationship with a woman who agrees to use acceptable contraception as outlined in inclusion criterion #7, and/or abstinence from sexual intercourse with women.*

9. Women of childbearing potential must have a negative urine pregnancy test within 24 hours prior to receipt of study product.

Participant Inclusion Criteria for Patients with Renal Impairment (Groups 2-4)

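### Read literally, the eligibility definition of childbearing potential omits a non-sterilised premenopausal woman without current menses, so the pre-dose pregnancy tests do not clearly apply to her

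*Protocol*

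**What the plan says.** Footnote 2 in Protocol 5.1.1.1 (renal groups) and 5.1.1.2 (controls) defines a woman of childbearing potential by two conditions. She has had none of the listed sterilising procedures, and she is "still menstruating or <1 year has passed since the last menses if menopausal". SAP 4.3.1 repeats the footnote in both of its lists ("1 year has passed since the last menses if menopausal").

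The pregnancy paragraph of Protocol 2.3.1 uses the same term with a different gloss: "females of childbearing potential, i.e., women who have started menses, must agree to use an effective method of birth control". That sentence refers the reader to Section 5.1.1.

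These requirements depend on the term:
- the contraception criterion (renal inclusion 8, control inclusion 7);
- the test shortly before dosing (renal inclusion 10: "Women of childbearing potential must have a negative urine pregnancy test within 24 hours prior to receipt of study product"; control inclusion 9 is the same);
- control exclusion 13: "Women of childbearing potential with a positive urine pregnancy test within 24 hours prior to receipt of study product";
- the scheduled urine tests at Visits 00B (6.1.2), 00C (6.1.3), 01A (6.2.1) and 02 (6.3.3), and at early termination (6.5), restated in 7.2.1, Appendix A footnote 4 and SAP 9.6.

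Two criteria on pregnancy are not limited by the term. Renal exclusion 15 applies to women generally and bars one where the "participant is pregnant (positive test for urine Human Chorionic Gonadotropin [HCG]) at screening or Admission". Control inclusion 3 reads "Are healthy male or non-pregnant female, between the ages of 18 and 85 years, inclusive".

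**The concern.** One defined term decides who is tested before dosing, and the definition attached to eligibility turns on whether a woman is menstruating now. Absent menses in a premenopausal woman can be a sign of early pregnancy. A site that follows the footnote to the letter could therefore leave untested a woman for whom the test is meant. Every participant receives pretomanid, Section 2.3.1 says its risk to an unborn child is not known, and Section 2.3.2 says participants gain no direct benefit. Section 5 allows no exemptions from the criteria, and two sites must apply the same words in the same way. A second wording of the term in 2.3.1 does not help them do so.

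**Working it through.** No sample size, power or error-rate figure bears on this point. The check sets the two wordings side by side and then traces what depends on the term.

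**Step 1. Who is included (women past menarche)**

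| Woman | 2.3.1 gloss | Footnote 2, literal |
|---|---|---|
| Not sterilised, menstruating | yes | yes |
| Not sterilised, menopausal, under 1 year since last menses | yes | yes |
| Not sterilised, menopausal, 1 year or more | yes | no |
| Sterilised, menstruating | yes | no |
| Sterilised, not menstruating | yes | no |
| Not sterilised, premenopausal, no current menses | yes | **no** |

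The wordings differ in 4 of 6 rows. In three of the four (sterilised, or a year or more past menopause) the footnote gives the sensible answer and 2.3.1 is merely too broad. Only the last row is a gap in a safeguard. That woman fails the first branch because she is not menstruating, and the second because its one-year limit applies only to a menopausal woman.

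**Step 2. What was probably meant**

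Footnote 2 sets menstruating against menopausal, which suggests that the first branch stands for *not yet menopausal*. Footnote 3 points the same way: it lists "licensed hormonal methods such as implants, injectables, or oral contraceptives" as acceptable for women of childbearing potential, with no condition on current menses. The wider gloss in 2.3.1 agrees. The footnote itself does not say so.

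**Step 3. Tests required for the woman in the last row**

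| Reading | Pre-dose (00B, 00C, 01A) | Visit 02 | Early termination, if it occurs |
|---|---|---|---|
| 2.3.1 gloss | 3 of 3 | yes | yes |
| Footnote 2 as *not yet menopausal* | 3 of 3 | yes | yes |
| Footnote 2, literal | 0 of 3 | no | no |

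A completer has 3 + 1 = 4 scheduled tests, because the early-termination test applies only to those who leave the study. Only the three pre-dose tests can prevent exposure.

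**Step 4. What else would catch her**

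In the renal groups, exclusion 15 covers all women and names a urine HCG result at screening or admission, so a test is the natural way to verify it. The visits that perform the test limit it to women of childbearing potential. In the controls, inclusion 3 requires that she not be pregnant but names no test, and exclusion 13 is limited by the same term. The gap is therefore widest in the controls: 6 in Group 1A, plus 6 + 6 = 12 in Groups 1B and 1C only if Part B opens. These counts include men.

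A woman without menses who already uses a method in footnote 3 meets the contraception standard, so for her only the testing is unclear.

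**The case against.** The strongest reply is that no clinician would read footnote 2 this way. To omit this woman, a site must decide that she is not menopausal and yet not of childbearing potential. The criteria are assessed by a licensed clinician, and questions about eligibility go to the sponsor's medical officer (Section 5). Renal exclusion 26 and control exclusion 23 let the investigator exclude for safety, the history covers the reproductive tract (7.1), a repeat test is allowed if the participant suspects pregnancy (6.6), and pregnancy is asked about at Visit 03 (6.4).

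Much of this stands. The narrow reading is probably unintended, and together these provisions make an undetected exposure unlikely. But none of them schedules a pre-dose test for her, the Visit 03 call comes after dosing, and a site that takes the footnote at its word has no reason to raise a question.

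A reader might also infer that the two sections conflict in both directions, so that sites would have to demand contraception of sterilised and postmenopausal women. The documents do not support that. Section 2.3.1 is a description of risk that defers to 5.1.1, so its breadth is only an inconsistency.

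**Conclusion.** The point holds as minor safety wording. The textual omission is certain. That a site would act on it is a possibility and rests on a literal reading that was probably not intended. Under that reading a non-sterilised premenopausal woman without current menses has 0 of 3 pre-dose tests required instead of 3 of 3. The documents do not give the number of such women, and it is probably few.

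Two larger inferences should be resisted. The protocol does not admit women known to be pregnant: renal exclusion 15 and control inclusion 3 bar them, and the gap lies only in who must be tested and use contraception. Nor is it right to count five missed tests for each woman or 18 assured controls: the early-termination test is conditional, and only 6 controls are certain unless Part B opens. Sample size, PK analysis and the rule for opening Part B are untouched.

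**What to change.** In Protocol 5.1.1.1 and 5.1.1.2, reword footnote 2 to: *Not permanently sterilised (existing list unchanged) and not postmenopausal (postmenopausal = at least 1 year since last menses due to menopause), regardless of current menstruation.*

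In 2.3.1, replace the gloss about having started menses with: *as defined in footnote 2 of Section 5.1.1.*

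The tests at 00B, 00C, 01A, 02 and early termination then follow one definition, and the visit schedule needs no edit. The clinician must still judge whether absent menses are due to menopause, as now. Update the two copies in SAP 4.3.1 for consistency only, since the protocol governs enrolment and testing.

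The cost is amendment wording in three protocol places, the matching SAP text, and at most a few extra urine tests.
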